### *[ $^{14}\text{C}$ ]-CHF6001 IV infusion:*

- Detailed information on the process for formulation preparation are in the pharmacy protocol. The IV formulation will be administered intravenously as a single dose over 15 minutes, ending at the expected  $T_{\text{max}}$  of 2 h for the inhaled dose giving a total infused dose of 18.5 $\mu$ g and 500nCi (18.5kBq).

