#### 7.2.1.1 Determination of CHF6001 and related analytes in human plasma

Blood samples for the determination of plasma total [C], [C]-CHF6001, metabolite profiling (if required) and non-radiolabeled CHF6001, will be collected and processed according to an established laboratory manual at pre-dose and in the 0-240h interval after dosing, as follows:

- 22 blood samples of 4 mL for plasma non-radiolabeled CHF6001 will be collected at pre-dose (within 60 min from inhaled dosing) and at the following timepoints post inhaled dose: 15, 30, 60, 90 min, 2, 3.75, 5.75, 7.75, 9.75, 11.75, 13.75, 25.75, 49.75, 73.75, 97.75, 121.75, 145.75, 169.75, 193.75, 217.75 and 241.75 hours;
- 25 blood samples of 5 mL for plasma total [C] and [C]-CHF6001 will be collected at pre-dose (within 60 min from inhaled dosing) and at the following timepoints relative to the start of the IV infusion: 5, 10, 15 [end of infusion], 20, 25, 30, 45, 60 min, 2, 4, 6, 8, 10, 12, 24, 48, 72, 96, 120, 144, 168, 192, 216 and 240 hours;
- 25 blood samples of 10 mL for plasma [C] of the relevant metabolites will be collected at pre-dose (within 60 min from inhaled dosing) and at the following timepoints relative to the start of the IV infusion: 5, 10, 15 [end of infusion], 20, 25, 30, 45, 60 min, 2, 4, 6, 8, 10, 12, 24, 48, 72, 96, 120, 144, 168, 192, 216 and 240 hours;
- 2 blood samples of 2 mL for whole blood total [C] and [C]-CHF6001 will be collected at pre-dose (within 60 min from inhaled dosing) and 20 min after the start of infusion (for a total of 4 samples).

The processing, storage and shipment of samples are detailed in the laboratory manual document.

Day	Clock time (exemplary)	Time after inhaled administration	Time after start of i.v. administration	Time deviation allowed	PK timepoint inhaled administration	PK timepoint i.v. administration
1	08:00	Pre-dose		Within 60 minutes from inhalation	X 	X 

Clinical Study Code: CLI-06001AA1-02	Version No.: 1.0
EUDRACT No.: 2020-004201-31	Date: 19 October 2020

	09:00	Start of inhaled administration			
	09:15	15 min	± 2 min	X 	
	09:30	30 min	± 2 min	X 	
	10:00	60 min	± 5 min	X 	
	10:30	90 min	± 5 min	X 	
	10:45		Start of infusion (SOI)		
	10:50		SOI + 5 min	± 2 min	X 
	10:55		SOI + 10 min	± 2 min	X 

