
- $AUC_{0-t}$ : the area under the concentration-time curve from 0 to the last quantifiable concentration will be computed using the linear trapezoidal rule with linear interpolation;
- $AUC_{0-\infty}$ : the area under the concentration-time curve extrapolated to infinity will be calculated as the sum of  $AUC_{0-t}$  and a residual part extrapolated to infinite time. The residual area from the last concentration data point to infinite time is calculated using the approximation:

$$\int_t^{\infty} C_t dt = C_t / \lambda z$$

Where  $\lambda z$  is the first order terminal rate constant, estimated by linear regression of the terminal log-linear segment of the plasma log-concentration curve, and  $C_t$  is the last quantifiable concentration data point. In order to determine  $\lambda z$  by log-linear regression, at least 3 points will be used. The quality of log-linear regression and the reliability of extrapolated PK parameters should be demonstrated by an adjusted coefficient of determination  $R^2$  of at least 0.85;

- $C_{max}$  and  $t_{max}$ : the value and time of the maximum concentration will be obtained directly from the experimental data without interpolation;
- $t_{1/2}$ : the terminal half-life, associated with negative slope ( $-\lambda z$ ), calculated as  $0.693/\lambda z$  from the individual drug concentrations versus time profiles.
- $Dose_{IV}$ : is the actual IV dose calculated as [weight of full syringe (g) minus syringe weight after dose (g)] multiplied by nominal concentration ( $\mu\text{g/g}$ )
- $F_{inh}$ : inhaled absolute bioavailability based on  $AUC_{(0-\infty)}$  for CHF6001 calculated as  $F_{inh} = (AUC_{0-\infty\_inh} \times Dose_{IV}) / (AUC_{0-\infty\_IV} \times Dose_{inh})$ . If  $AUC_{0-\infty}$  is not calculable  $AUC_{0-t}$  will be used.
- $R_{b/p}$ : whole blood to plasma ratio is determined on the [C]-CHF6001 whole blood and plasma concentration ( $C_b$  and  $C_p$ ) 20 min after the start of infusion, calculated as  $R_{b/p} = C_b / C_p$
- $R_{bt/pt}$ : whole blood to plasma ratio is determined on the total-[C] whole blood and plasma concentration ( $C_{bt}$  and  $C_{pt}$ ) 20 min after the start of infusion, calculated as  $R_{bt/pt} = C_{bt} / C_{pt}$
- $CL$ : the total body plasma clearance following IV administration, calculated only for [C]-CHF6001 as  $Dose_{IV} / AUC_{0-\infty}$

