- $CL_{blood}$ : the total body blood clearance following IV administration, calculated only for [C]-CHF6001 as  $CL_{blood} = CL / R_{b/p}$
- $V_{dss}$ : Volume of distribution at steady-state will be calculated only for [C]-CHF6001 as  $Dose_{IV} \times AUMC_{0-\infty} / (AUC_{0-\infty})^2$

Clinical Study Code: CLI-06001AA1-02	Version No.: 1.0
EUDRACT No.: 2020-004201-31	Date: 19 October 2020

- $V_z$ : the volume of distribution during the terminal phase, calculated only for [C]-CHF6001 as  $Dose_{IV}/(AUC_{0-\infty} \times \lambda_z)$
- $Fr_{plasma}$ : fraction of the relevant metabolites in plasma calculated as  $100 \times AUC [^{14}C]\text{-metabolite}/AUC [^{14}C]\text{-total radioactivity}$

The following PK parameters will be calculated, whenever possible, for each subject based on the concentrations of urine [C]-CHF6001 and urine [C]-total radioactivity:

- $Ae_u$ : amount excreted in urine (expressed in weight) over sampling interval calculated as:  $Ae_u = C_{ur} \times V_{ur}$ , where  $C_{ur}$  is the concentration in urine and  $V_{ur}$  is the volume of urine
- Cumulative  $Ae_u$ : cumulative amount excreted in urine, calculated as the sum of the amount excreted in urine for each collection period
- $fe_u$ : percent of the dose excreted in urine over a sampling interval, where  $fe_u = 100 \times (Ae_u/Dose_{IV})$
- $Fe_u$ : cumulative percent of dose excreted in urine, calculated as the sum of the percent of dose excreted in urine for each collection period
- $CL_R$ : renal plasma clearance calculated only for [C]-CHF6001, if plasma  $AUC_{0-\infty}$  is calculable then  $CL_R = \text{Cumulative } Ae_u/AUC_{0-\infty}$ , if Plasma  $AUC_{0-\infty}$  is not calculable then  $CL_R = \text{Cumulative } Ae_u/AUC_{0-t}$ .
- $CL_{R\_blood}$ : renal blood clearance calculated only for [C]-CHF6001, where  $CL_{R\_blood} = CL_R/R_{b/p}$
- $Fr_{urine}$ : fraction of the relevant metabolites recovered in urine calculated as amount recovered ( $Ar_u$ )/ $Dose_{IV} \times 100$

The following PK parameters will be calculated, whenever possible, for each subject based on plasma [C]-CHF6001 and urine [C]-CHF6001 radioactivity:

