Plasma [¹⁴C]-CHF6001 and [¹⁴C]-total radioactivity

Parameter	Units ^a	Definition
[¹⁴ C]- CHF6001 and [¹⁴ C]- Total	AUC _(0-t) _iv	h*xg/mL area under the concentration-time curve from 0 to the last quantifiable concentration (t _{last}) ^b
[¹⁴ C]- CHF6001 and [¹⁴ C]- Total	AUC _(0-∞) _iv	h*xg/mL area under the concentration-time curve extrapolated to infinity ^c
[¹⁴ C]- CHF6001 and [¹⁴ C]- Total	%AUC _{extrap}	% percentage of AUC due to extrapolation from the last quantifiable concentration to infinity
[¹⁴ C]- CHF6001 and [¹⁴ C]- Total	C _{max_iv}	xg/mL the value of the maximum observed concentration
[¹⁴ C]- CHF6001 and [¹⁴ C]- Total	t _{max_iv}	h the time of the maximum observed concentration
	t _{last_iv}	h the time of the last quantifiable concentration
[¹⁴ C]- CHF6001 and [¹⁴ C]-Total	t _{1/2_iv}	h terminal half-life
[¹⁴ C]- CHF6001	CL	L/h total body plasma clearance (plasma [¹⁴ C]-CHF6001)
[¹⁴ C]- CHF6001	V _z	L volume of distribution during the terminal phase (plasma [¹⁴ C]-CHF6001)
[¹⁴ C]- CHF6001	V _{dss}	L volume of distribution at steady state (plasma [¹⁴ C]-CHF6001)
Plasma concentration of [¹⁴ C]-CHF6001/Total Radioactivity Ratio	NA	ratio of plasma concentration of [¹⁴ C]-CHF6001 to plasma concentration of [¹⁴ C]-total
AUC _(0-∞) Plasma [¹⁴ C]-CHF6001/Total Radioactivity Ratio	NA	AUC _(0-∞) of plasma [¹⁴ C]-CHF6001 relative to AUC _(0-∞) of plasma [¹⁴ C]-total radioactivity
C _{max} Plasma [¹⁴ C]-CHF6001/Total Radioactivity Ratio	NA	C _{max_iv} of plasma [¹⁴ C]-CHF6001 relative to C _{max_iv} of plasma [¹⁴ C]-total radioactivity

^a Units are based on concentration units (provided by the bioanalytical lab or preferred units for presentation of PK parameters) and dose units used in the study. For total radioactivity, C_{max} and AUC units will be presented as mass equivalents (ng Eq/g and h*ng Eq/g, respectively).

^b Area under the concentration-time curve will be calculated using the linear trapezoidal rule with linear interpolation

^c Based on the last observed quantifiable concentration

Blood [¹⁴C]-CHF6001 and [¹⁴C]-total radioactivity

Parameter	Units	Definition
[¹⁴ C]-CHF6001	R _{b/p}	NA whole blood to plasma ratio is to be determined on the [¹⁴ C]-CHF6001 whole blood and plasma concentration (C _b and C _p) 20 minutes after the start of infusion, calculated as R _{b/p} = C _b /C _p

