10.5 Laboratory Data

Quantitative chemistry and haematology parameters and fasting glucose values will be summarized descriptively at screening and discharge. Shift tables from screening with reference to normal ranges will be presented.

Serology and urinalysis results will only be listed.

Abnormal laboratory data will be flagged in the listings.

11 Other Analyses

No other analyses planned.

12 Changes in the Planned Analyses from Study Protocol

There are no changes to the protocol defined analysis.

13 Output

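### The protocol's Vdss formula is the bolus form and lacks the infusion-time term, although the tracer is infused over 15 minutes; the net direction of error in the reported Vdss is not established

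*Protocol*

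**What the plan says.** Protocol section 8 gives Vdss as "Dose_{IV} \times AUMC_{0-\infty} / (AUC_{0-\infty})^2" and restricts it to the tracer: "Volume of distribution at steady-state will be calculated only for" [14C]-CHF6001. No input-time term appears. CL is defined just before it ("the total body plasma clearance following IV administration, calculated only for" [14C]-CHF6001) as intravenous dose over AUC to infinity.

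The input is not a bolus. Protocol section 6.2.2 says "The IV formulation will be administered intravenously as a single dose over 15 minutes", and section 7.2.1.1 places the tracer samples at "timepoints relative to the start of the IV infusion: 5, 10, 15 [end of infusion], 20, 25, 30, 45, 60 min" and later, out to 240 h. Three of those samples fall during the infusion or at its end.

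Section 8 also fixes the linear trapezoidal rule with linear interpolation for AUC. It names no rule for AUMC.

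SAP section 9.1 lists the parameter as "volume of distribution at steady state", obtained by noncompartmental methods in Phoenix WinNonlin, and gives no formula. SAP section 12 states "There are no changes to the protocol defined analysis". Neither document mentions MRT, mean input time or an infusion correction.

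**The concern.** When drug enters over a finite time, the mean time that the concentration curve measures includes the time spent entering. For a constant-rate infusion this adds half the infusion duration. Multiplying the uncorrected mean time by CL credits that delay to distribution volume. The term is positive in every subject, so averaging over 8 subjects does not remove it.

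Vdss is a listed PK variable in both documents, and protocol section 1.3 says that the compound has not been infused in humans before. This would be the first human estimate after intravenous dosing. The written definition should therefore match the way the drug is given.

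**Working it through.** **Inputs**
- T = 15 min = 0.25 h (Protocol 6.2.2). Time zero is the start of infusion (Protocol 7.2.1.1).
- Nominal intravenous dose 18.5 µg (Protocol 6.2.2). It cancels from the relative size.
- CL, Vss and MRT have no values in the documents, so every figure that uses them rests on an assumption. There is no stated Vdss to reproduce.

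**The missing term**
- For a constant infusion timed from its start: AUMC/AUC = MRT + T/2.
- True value: Vss = CL × MRT = CL × (AUMC/AUC − T/2).
- Protocol formula: Dose × AUMC/AUC² = CL × AUMC/AUC = Vss + CL × T/2.
- T/2 = 0.25/2 = 0.125 h, so the extra term is CL × 0.125 h.
- Since Vss = CL × MRT, the term relative to Vss is 0.125 h/MRT.

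| Assumed MRT (h) | 0.125/MRT |
|---|---|
| 1 | 12.5% |
| 2 | 6.3% |
| 5 | 2.5% |
| 8 | 1.6% |
| 20 | 0.6% |
| 42 | 0.3% |

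In litres, assumed CL of 5, 20 and 87 L/h gives 0.625, 2.5 and 10.9 L. The last is the hepatic blood flow quoted in Protocol section 8, used only as a high illustration.

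**Check by integration, then with the planned sampling**

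Six assumed two-compartment models received 18.5 µg over 0.25 h. With exact integrals the protocol formula exceeded true Vss by CL × 0.125 h in each, and the corrected formula returned true Vss. The noiseless profiles were then sampled at the protocol times. The linear rule was used for both AUC and AUMC, all samples to 240 h were taken as quantifiable, and the terminal slope was taken as known.

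| CL (L/h) | True Vss (L) | MRT (h) | Exact, protocol formula (L) | Sampled, protocol formula (L) | Sampled, T/2 subtracted (L) |
|---|---|---|---|---|---|
| 10 | 200 | 20 | 201.25 | 183.1 (−8.4%) | 181.9 (−9.0%) |
| 20 | 400 | 20 | 402.5 | 367.6 (−8.1%) | 365.2 (−8.7%) |
| 40 | 400 | 10 | 405.0 | 364.5 (−8.9%) | 359.8 (−10.1%) |
| 87 | 400 | 4.6 | 410.9 | 391.0 (−2.3%) | 380.6 (−4.8%) |
| 20 | 100 | 5 | 102.5 | 92.2 (−7.8%) | 89.8 (−10.2%) |
| 40 | 40 | 1 | 45.0 | 41.8 (+4.6%) | 37.1 (−7.3%) |

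In five of the six models the sampled result is below the truth before any correction. The exception has an MRT of 1 h. In all six, subtracting T/2 under the linear rule leaves a larger error than before.

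A second set of runs, with an assumed quantification limit, agrees. At MRT 16.5 h (CL 20 L/h, Vss 330 L) the error was −9.4% uncorrected and −10.1% corrected. At MRT 42 h (CL 20 L/h, Vss 840 L) it was −6.4% and −6.7%.

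Repeating the six models with logarithmic trapezoids wherever concentration falls, for both AUC and AUMC, gives corrected values between −0.5% and −2.4% of the truth. The protocol formula under the same rule ranges from −1.5% to +11.9%.

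**The case against.** The strongest reply concerns what will actually be reported. A reader might infer that every Vdss will come out too high by CL × 0.125 h. The documents do not support that. The identity holds for exact integrals, whereas the plan fixes a linear rule for AUC and samples only every 24 h after the first day. In most of the assumed models the integration error is larger than the T/2 term and of opposite sign. This stands: the term is one component of the error, and net overstatement is not shown.

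Second, the SAP leaves the calculation to validated software and writes no formula. The documents do not show what the software's infusion setting computes, so a biased result cannot be asserted. This stands too, but it does not rescue the text. If the software applies the correction, the output departs from the protocol formula while SAP section 12 declares no change. If it does not, the extra term remains.

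Third, materiality. Vdss feeds no other parameter, and CL, Vz, F_inh, CL_R and E_h_blood do not use AUMC. Vdss is summarised descriptively in 8 subjects with no test or interval. Plasma sampling to 240 h suggests that slow elimination was expected, which points to the small end of the range. All of this stands, and it keeps the point minor.

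**Conclusion.** The formula as written is wrong for this mode of input. It contains an extra CL × T/2, which is CL × 0.125 h at nominal T, or 0.125 h/MRT relative to Vss. MRT is unknown, so the size can only be given as a range: 12.5% at 1 h, falling to 0.3% at 42 h. Only Vdss is affected, and the bioavailability and mass balance results are untouched.

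The sign and size of the net error in the reported Vdss are not established. They depend on the AUMC integration rule, the quantification limit, the true disposition and the software setting, none of which can be fixed from the documents. The simulation results rest on assumed two-compartment models without noise. This is a correction worth making to the definition, with no consequence for the trial's main conclusions.

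**What to change.** State in the SAP section 9.1 parameter table and in protocol section 8:

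Vdss = CL × (AUMC0-∞/AUC0-∞ − T/2)

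- Time runs from the start of infusion. AUMC depends on its origin, and the planned listing of sampling times is relative to inhalation.
- T is each subject's actual infusion duration. If an infusion is interrupted, which SAP section 8.6 foresees, use the actual mean input time in place of T/2.
- State the AUMC integration rule alongside, for example linear-up/log-down. Under the linear rule the T/2 correction alone did not bring Vdss closer to the truth in the models above. AUMC and AUC should follow a consistent rule. A change to the AUC rule would also reach CL, Vz and F_inh, so it should be decided openly.
- Confirm that the software output reproduces this formula, and list the change in SAP section 12.

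The cost is one formula, one sentence on integration and a check of the software setting. No new samples or visits are needed. Infusion duration is probably already available: Protocol 6.2.3.2 has administration reported in the eCRF and SAP 8.6 lists the infusion variables. Neither names start and stop times expressly, so this should be confirmed.

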## 9. SAFETY ASSESSMENTS

The safety profile will be assessed through the monitoring of the following:

- **Adverse Events (AEs)** and **Adverse Drug Reactions (ADRs)**
- **Vital signs** (Systolic and Diastolic Blood Pressure). Vital signs will be evaluated pre-dose and at 2,5 hours post-dose
- Heart Rate (HR) from **local 12-lead safety ECG** will be performed at pre-dose and at 2,5 hours post-dose
- **Clinical laboratory evaluations**: Blood chemistry, haematology and fasting glucose collected at Screening and Discharge

## 10. ADVERSE EVENT REPORTING

### **10.1 Definitions**

An **Adverse Event** is “any untoward medical occurrence in a patient or clinical trial subject administered a medicinal product and which does not necessarily have a causal relationship with this treatment”.

An adverse event can therefore be any unfavorable and unintended sign (including abnormal laboratory finding), symptom, or disease temporally associated with the use of a medicinal product, whether or not considered related to the medicinal product.

An **Adverse Drug Reaction** is an “untoward and unintended responses to an investigational medicinal product related to any dose administered”.

All adverse events judged by either the reporting Investigator or the Sponsor as having a reasonable causal relationship to a medicinal product qualify as adverse reactions. The expression “reasonable causal relationship” means to convey in general that there are facts (evidence) or arguments meant to suggest a causal relationship.

The definition covers also medication errors and uses outside what is foreseen in the protocol, including misuse and abuse of the product.

A **Serious Adverse Event (SAE)/Serious Adverse Drug Reaction** is any untoward medical occurrence or effect that at any dose falls in one or more of the following categories:

#### **- Results in death**

Death is not an adverse event but an outcome. It is the cause of death that should be regarded as the adverse event. The only exception to this rule is “sudden death” where no cause has been established; in this latter instance, “sudden death” should be regarded as the adverse event and “fatal” as its reason for being serious.

Clinical Study Code: CLI-06001AA1-02	Version No.: 1.0
EUDRACT No.: 2020-004201-31	Date: 19 October 2020

- **Is life-threatening**

Life-threatening refers to an event in which the subject was at risk of death at the time of the event (e.g., aplastic anaemia, acute renal failure, and anaphylaxis). The term does not refer to an event which hypothetically might have caused death if it were more severe.

- **Requires hospitalisation or prolongation of existing hospitalisation**

Hospitalization refers to a situation whereby an AE is associated with unplanned formal overnight admission into hospital, usually for purpose of investigating and/or treating the AE. Hospitalization for the treatment of a medical condition that occurs on an “elective” or “scheduled” basis or for a pre-existing condition that did not worsen during the study should not necessarily be regarded as a AE. Complications that occur during the hospitalisation are AEs. If a complication prolongs hospitalisation, the event is an SAE. Emergency room visits that do not result in a formal admission into hospital should be evaluated for one of the other seriousness criteria (e.g., life-threatening; persistent or significant disability or incapacity; medically significant).

- **Results in persistent or significant disability or incapacity.**

The term significant disability should be viewed as any situation whereby an AE has a clinically important effect on the subject’s physical or psychological well-being to the extent that the subject is unable to function normally.

- **Is a congenital anomaly or birth defect**

- **Is a medically significant adverse event**

This criterion allows for any situations in which important adverse events/reactions that are not immediately life-threatening or do not result in death or hospitalisation may jeopardise the subject’s health or may require intervention to prevent one of the above outcomes.

Examples of such events are: intensive treatment in an emergency room or at home for allergic bronchospasm; blood dyscrasias or convulsions that do not result in hospitalisation; or development of drug dependency or drug abuse.

Medical and scientific judgment should be exercised in deciding whether an event is serious because medically significant.

Any suspected transmission via a medicinal product of an infectious agent is also considered a serious adverse reaction.

**A Non-Serious Adverse Event/Non-Serious Adverse Drug Reaction** is an adverse event or adverse drug reaction that does not meet the criteria listed above for a serious adverse event/serious adverse drug reaction.

## **10.2 Expectedness**

An expected adverse reaction is an adverse reaction, the nature or severity of which is consistent with the applicable reference safety information (included in the Investigator’s Brochure for CHF6001), otherwise it is considered unexpected.

Reports which add significant information on specificity or severity of a known, already documented serious adverse drug reaction constitute unexpected events. For example, an event more specific or more severe than described in the reference safety information would be considered as “unexpected”.

Clinical Study Code: CLI-06001AA1-02	Version No.: 1.0
EUDRACT No.: 2020-004201-31	Date: 19 October 2020

Examples of such events are: (a) acute renal failure as a labelled ADR with a subsequent new report of interstitial nephritis and (b) hepatitis with a first report of fulminant hepatitis.

### **10.3 Intensity of Adverse Event**

Each Adverse Event must be rated on a 3-point scale of increasing intensity:

**Mild:** The event causes a minor discomfort or does not interfere with daily activity of the subject or does not lead to either modification of test treatment dosage or establishment of a correcting treatment.

**Moderate:** The event perturbs the usual activity of the subject and is of a sufficient severity to make the subject uncomfortable. The event leads to a diminution of dosage of the test treatment, or a temporary interruption of its administration or to the establishment of a correcting treatment.

**Severe:** The event prevents any usual routine activity of the subject and causes severe discomfort. It may be of such severity to cause the definitive interruption of test treatment.

